6.12.7 Subsequent Chemoembolizations

To proceed with subsequent chemoembolization, study subjects must meet the following criteria:

- \leq Grade 2 hematologic toxicity with the exception of:
 - serum creatinine $\leq 1.5 \text{ mg/dl}$;
 - serum bilirubin $\leq 3.0 \text{ mg/dl}$.

Repeat Chemoembolization (for either ipsilateral or contralateral disease) if indicated, should be performed at least 4 weeks apart. Up to 4 chemoembolizations can be performed in 6 months of the first chemoembolization. Additional chemoembolizations, if clinically indicated can occur after the first 6 months

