6.3 LEE011 ADMINISTRATION SCHEDULE AND DOSE ADJUSTMENTS

LEE011 will be given orally once a day on days 1-21 of a 28 day cycle (3 weeks on / 1 week off). Days 22-28 will be a “rest” from LEE011.

Table 6.1 Dose and Treatment Schedule

Study Treatment	Pharmaceutical form and route of administration	Total Dose	Frequency and/or Regimen
LEE011	200 mg capsules by mouth	200,400, or 600 mg	Once Daily on Days 1-21 of a 28 day cycle. Rest Days 22-28

LEE011 will be administered as a flat-fixed dose, and not by body weight or body surface area.

The investigators will instruct the patient to take the study drug as per protocol. Patients must be instructed to return unused study drugs to the site at discontinuation or completion of treatment. The site personnel will ensure that dosing compliance is being performed by reviewing patient dosing diaries at each the end/start of a new treatment cycle.

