Same grade as baseline or increase from baseline grade 0 to grade 1 (confirmed 48 to 72 hrs later)	No dose adjustment required with LFTs monitored per protocol if same grade as baseline or bi-weekly in case of increase from baseline grade 0 to 1

Increase from baseline grade 0 or 1 to grade 2 ($> 3.0 - 5.0 \times \text{ULN}$) or from baseline grade 2 to grade 3 ($> 5.0 - 20.0 \times \text{ULN}$)
	
Dose interruption of LEE011
 
If resolved to \leq baseline value in ≤ 21 days, then maintain dose level
 
If resolved to \leq baseline value in > 21 days or toxicity recurs, discontinue LEE011

Increase from baseline grade 0 or 1 to grade 3 ($> 5.0 - 20.0 \times \text{ULN}$)
	
Discontinue LEE011

Grade 4 ($> 20.0 \times \text{ULN}$)
	
Discontinue LEE011

AST or ALT and concurrent Bilirubin
	

AST or ALT \geq grade 2 ($> 3 \times \text{ULN}$) in patients with normal values at baseline and total bilirubin $> 2 \times \text{ULN}$ o r AST or ALT \geq grade 3 ($> 5 \times \text{ULN}$) in patients with grade 1 or 2 at baseline, and total bilirubin $> 2 \times \text{ULN}$
	
Discontinue LEE011

Confounding factors and/or alternative causes for increased transaminases should be excluded before dose interruption/reduction. They include but are not limited to: concomitant medications, herbal preparations or dietary supplements, infection, hepato-biliary disorder or obstruction, new or progressive liver metastasis, and alcohol intake.
	

Table 6-6 LEE011 dose modification guidance in case of QT PROLONGATION

The ECG are done based on scheduled assessment as detailed in table 7.1.

QTC	
Grade	Dose Modification
For all grades	
 • Check the quality of the ECG • Perform analysis of serum electrolytes (K+, Ca++, Phos, Mg++). If below the lower limit of normal, interrupt LEE011 administration, correct with supplements or appropriate therapy as soon as possible, and repeat electrolytes until documented as normal • Review concomitant medication usage for the potential to inhibit CYP3A4 and/or to prolong the QT interval • Check compliance with correct dose and administration of LEE011
1 QTc 450-480 ms	No dose adjustment required.

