2 QTc 481-500 ms	
Interrupt LEE011
 
Perform a repeat ECG one hour after the first QTcF of ≥ 481ms
 
If QTcF < 481 ms, restart LEE011 at the same dose. No dose adjustment for the first occurrence
 
If QTcF remains ≥ 481 ms, restart LEE011 at the same dose level. No dose adjustments required for the first occurrence
 
If QTcF ≥ 481 ms recurs, discontinue LEE011
 
Repeat ECGs 7 days and 14 days after dose resumption (then as clinically indicated) for any patient who has therapy interrupted due to QTcF ≥ 481 ms

3 QTc ≥ 501 ms on at least two separate ECGs	
Interrupt LEE011
 
 • Consider consulting a local cardiologist • Perform a repeat ECG one hour after the first QTcF of ≥ 501 ms • If QTcF remains ≥ 501 ms, repeat ECG as clinically indicated, but at least once a day until the QTcF returns to < 481 ms.

	
 If QTcF returns to < 481 ms, LEE011 should be reduced by 1 dose level. (please refer to the dosing schedule table) 
Repeat ECGs 7 days and 14 days after dose resumption for any patient who has therapy interrupted due to QTcF \geq501 ms
 
 If QTcF of \geq 501 ms recurs, discontinue LEE011

4 QT/QTc \geq 501 or $>$ 60 ms change from baseline
 
And
 
Torsades de pointes or polymorphic ventricular tachycardia, or signs/symptoms of serious arrhythmia
	Discontinue LEE011

Table 6-7 LEE011 Dose Adjustment and Management Recommendations for ALL OTHER ADVERSE REACTIONS

Grade	Dose Adjustment and Management Recommendations
1	No dose adjustment recommended. Initiate appropriate medical therapy and monitor.
2	
Dose interruption until recovery to grade \leq1. Initiate appropriate medical therapy and monitor.
 
Re-initiate LEE011 at the same dose.
 
 If the same toxicity recurs at grade 2, interrupt LEE011 until recovery to grade \leq1. Re-initiate LEE011 at the next lower dose level.

3	
Dose interruption until recovery to grade ≤ 1. Initiate appropriate medical therapy and monitor.
 
Re-initiate LEE011 at the next lower dose level.
 
 • If toxicity recurs at grade 2: temporary dose interruption until recovery to grade ≤ 1 and reduce LEE011 dose the next lower dose level. • If toxicity recurs at grade 3, discontinue LEE011.
4	Discontinue LEE011 and treat with appropriate medical therapy.

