 - Physical examination
 - Comprehensive metabolic panel
 - Complete blood count without differential
 - Prothrombin time/INR

At this time the decision will be made to initiate LEE011 treatment.

LEE011 ADMINISTRATION WITH CHEMOEMBOLIZATION

Subjects are to be evaluated from toxicity with:

- Physical Examination (PE)
- Comprehensive Metabolic Panel (CMP)
- CBC
- ECG's

LEE011 will be initiated at the earliest of 7 days following embolization chemoembolization provided the following criteria are met:

- Serum bilirubin elevation $< 2.0 \times \text{ULN}$. If serum bilirubin $\geq 2.0 \times \text{ULN}$ then subjects will be assessed weekly and LEE011 will be initiated once bilirubin $< 2.0 \times \text{ULN}$.
- Resolution of Grade < 3 non-hematologic toxicity (other than bilirubin criteria above). If non-hematologic toxicity \geq Grade 3 then subjects will be assessed weekly and LEE011 will be initiated once $<$ Grade 2;
- Hematological toxicity of \leq Grade 2. If hematologic toxicity \geq Grade 3 then subjects will be assessed weekly and LEE011 will be initiated once \leq Grade 2.

If baseline AST, ALT and alkaline phosphate are elevated post chemoembolization decrease to baseline grade is necessary to continue/initiate LEE011;

- ECOG performance status ≤ 2 ;
- Serum AST, ALT, and/or Alkaline Phosphate $< 5 \times \text{ULN}$.

If criteria is not met, subjects will be reevaluated in 5-7 day intervals. If study subjects are unable to meet the above LEE011 starting criteria following initial chemoembolization treatment within 28 days after treatment, they will be removed from the study.

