10.3 LABORATORY ASSESSMENTS

Hematology, chemistry, coagulation, urinalysis, and cholesterol panels are to be performed according to the visit schedule outlined in Table 7.1 and 10.1.

Table: 10.1: Clinical Laboratory Parameters Collection Plan

Test Category	Test Name
Hematology	Hemoglobin, Platelets, white blood cells with differential (neutrophils, lymphocytes, basophils, eosinophils, monocytes)
Chemistry	Albumin, alkaline phosphatase, ALT, AST, creatinine, potassium, sodium, glucose, direct bilirubin,

	total bilirubin, total protein, magnesium, phosphorus
Cholesterol and Lipid Panel	Total cholesterol, LDL, HDL, triglycerides
Coagulation	PT, INR
Urinalysis	Glucose, protein, bilirubin, red blood cells, white blood cells, crystals, and bacteria.

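### Section 6.12.7 lists creatinine and bilirubin as exceptions to a hematologic limit, and sets no liver-enzyme, other non-hematologic or ECOG limit for a repeat chemoembolization

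*Combined protocol and SAP*

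**What the plan says.** Section 6.12.7 gives the criteria that must be met before a further TACE. The only graded one is an upper limit of "Grade 2 hematologic toxicity with the exception of" creatinine up to 1.5 mg/dl and bilirubin up to 3.0 mg/dl. The section otherwise requires a clinical indication, at least four weeks between procedures, and no more than four procedures in six months (more later if indicated).

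Table 10.1 in section 10.3 shows how the protocol classes these tests. Its Hematology row lists "Hemoglobin, Platelets, white blood cells with differential". Its Chemistry row begins "Albumin, alkaline phosphatase, ALT, AST, creatinine, potassium, sodium, glucose, direct bilirubin" and goes on to total bilirubin.

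Immediately before 6.12.7, an unnumbered block on giving LEE011 with chemoembolization sets fuller conditions. It counts bilirubin as non-hematologic, referring to "non-hematologic toxicity (other than bilirubin criteria above". It also has a hematologic limit, an ECOG limit of 2, and a line for "Serum AST, ALT, and/or Alkaline Phosphate" below 5 x ULN. These conditions govern starting or continuing LEE011.

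**The concern.** An exception has to belong to the class it is taken from, and creatinine and bilirubin are not hematologic. The sentence is therefore misworded on its face, and the possible corrections give different rules:

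- **As written:** blood counts, creatinine and bilirubin are limited; enzymes, other non-hematologic toxicity and ECOG are not.
- **If non-hematologic was meant:** the exceptions make sense, but the blood-count limit disappears, although section 9.1 lists grade 3 and 4 neutropenia and thrombocytopenia for LEE011.
- **If both classes were meant:** AST and ALT are capped at grade 2, but the text does not say so.

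Two investigators could decide differently on the same patient and both follow the protocol. Repeat TACE is part of study treatment (section 6.2). Raised liver enzymes are expected after TACE (section 9.2) and listed for LEE011 (section 9.1). Section 6.6 also records that TACE-related toxicity, not dose-limiting, led to specific rules for cohort 1 after discussion with the FDA.

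**Working it through.** The plan gives no figure to reproduce. The check is to set the three groups of limits side by side and then follow one patient through them.

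| Item | Entry (5.1) | Start of LEE011 after TACE (block before 6.12.7) | Repeat TACE (6.12.7) |
|---|---|---|---|
| Hematologic | counts at entry | grade 2 or lower | grade 2 or lower |
| Creatinine | 1.5 mg/dl or less, or clearance at least 50 mL/min | no separate line | 1.5 mg/dl or less |
| Bilirubin | 2.0 x ULN or less (separate direct-bilirubin rule in Gilbert's) | below 2.0 x ULN | 3.0 mg/dl or less |
| AST, ALT, alkaline phosphatase | below 5 x ULN | below 5 x ULN, and back to baseline grade if raised | none |
| Other non-hematologic | not compared | graded rule | none |
| ECOG | 0 to 2 | 2 or lower | none |

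Count in 6.12.7: one hematologic limit and two chemistry ceilings; none for enzymes, other non-hematologic toxicity or ECOG.

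Other places where such a limit might sit:

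- Tables 6-4 to 6-7 (section 6.7) act on LEE011 only.
- The DLT table (section 6.6) counts events related to LEE011 in its first cycle.
- The bead contraindications (section 6.12.1) are vascular or procedural, with no laboratory or ECOG threshold.
- Table 7.1 and its footnotes schedule tests but attach no threshold for proceeding to TACE.

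One patient, step by step:

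1. Baseline AST or ALT is grade 2, which Table 6-5 gives as above 3.0 and up to 5.0 x ULN. Entry requires below 5 x ULN, so such a patient is eligible.
2. On treatment the value rises to grade 3, above 5.0 and up to 20.0 x ULN, with bilirubin no higher than 2 x ULN. The whole grade 3 band lies above the 5 x ULN limit used both at entry and for starting LEE011.
3. The row in Table 6-5 that covers a rise "or from baseline grade 2 to grade 3" interrupts LEE011 and allows 21 days to return to baseline before the drug is stopped. The DLT table has the same interruption in cycle 1 of phase Ib.
4. Under 6.12.7, if bilirubin is at most 3.0 mg/dl, creatinine at most 1.5 mg/dl, hematologic toxicity at most grade 2 and four weeks have passed, every laboratory and spacing criterion for another TACE is met. The enzyme value that holds the drug does not enter the decision.

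Table 6-7 gives a wider parallel in phase II and in phase Ib from cycle 2. For other adverse reactions at grade 3 the action begins "Dose interruption until recovery to grade" 1 or lower. Section 6.12.7 has no matching condition for TACE.

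**The case against.** The strongest reply is that the protocol leaves TACE to standard of care on purpose. Sections 6.2 and 6.12 call it that, patients are reviewed in a multidisciplinary clinic, and numeric rules are kept for the investigational drug. On that view the fault is one wrong word. This stands in part: matching every drug rule with a TACE rule would be a preference. But the protocol chose to write mandatory criteria here, and those must be coherent.

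A reader might infer that only clinical judgement protects the patient. The documents do not support that:

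- Section 6.5 ends treatment for unacceptable toxicity, or for toxicity that interrupts treatment for more than four weeks. Since study treatment is the combination, this reaches TACE.
- Sections 6.6 and 9.4 stop enrollment after two related grade 5 events, or two related grade 4 events lasting at least 7 days.
- Footnote 2 of Table 7.1 requires examination, CMP, CBC and PT/INR every other week for two cycles after each TACE.
- Section 6.12.7 says repeat TACE is done if indicated, and section 7.4.1.1 allows withdrawal for an adverse event or by physician decision.

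These are real safeguards, but none is a per-procedure enzyme or ECOG limit.

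A reader might also use Table 7.1 to name the days on which a repeat TACE would fall within a drug hold. That does not work. The table marks TACE at Cycle 1 Day 1, although LEE011 starts at least 7 days after the first TACE, and footnote 13 lets the post-TACE visit serve as Day 1 of a cycle. The marks are not procedure dates.

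Nor does the worked case cover every patient with grade 3 enzymes. A rise from baseline grade 0 or 1 to grade 3, or any grade 4 value, ends LEE011 outright, so the conflict between a held drug and a permitted TACE does not arise.

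**Conclusion.** Wrong as written. Section 6.12.7 misstates the class to which its exceptions belong, and as it stands it sets no per-procedure limit on AST, ALT, alkaline phosphatase, other non-hematologic toxicity or ECOG. The creatinine and bilirubin ceilings do operate, so it would be too strong to say that liver function is unchecked before a repeat TACE.

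The enzyme example applies to patients with baseline grade 2 AST or ALT who reach grade 3 with bilirubin, creatinine and blood counts in range. The documents do not give their number. The conclusion rests on the text alone: that 6.12.7 is the only place with per-procedure toxicity criteria for repeat TACE, and that the limits just before it govern LEE011. That the author meant non-hematologic, or both classes, is plausible but is an inference. This is a safety-rule fault; sample size, significance level and power are unaffected. It should be fixed.

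**What to change.** Replace the criterion in 6.12.7 with:

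*Hematologic toxicity grade 2 or lower and treatment-related non-hematologic toxicity grade 2 or lower; AST, ALT and alkaline phosphatase below 5 x ULN; serum creatinine 1.5 mg/dl or lower; serum bilirubin 3.0 mg/dl or lower; ECOG 2 or lower.*

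The enzyme and ECOG limits match those for entry (section 5.1) and for starting LEE011, so they shut out no eligible patient at baseline. Restricting the non-hematologic limit to treatment-related events avoids deferring a standard procedure for unrelated grade 3 findings.

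The change is a one-sentence amendment. Table 7.1 already collects CMP, CBC and ECOG at the visits where TACE is marked, so no new assessment is needed. The price is that some repeat TACEs will wait until enzymes or other treatment-related grade 3 events recover. Enzyme rises are expected after TACE, so some deferrals should be anticipated; the documents do not allow their number to be estimated.

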6.6 DOSE LIMITING TOXICITIES-PHASE IB COMPONENT

The phase Ib component of the study will consist of 3+3 dose escalation rule with the dose of LEE011 escalating up to 600mg daily to determine the maximum tolerated dose (MTD) that will be used during the phase II component. The dose levels for the phase Ib aspect will be 200 mg, 400 mg, or 600 mg daily.

Only the first cycle of therapy (one cycle equals to one month) will be used to determine dose limiting toxicity (DLT). However, if two total grade 5 adverse events or 2 Grade 4 adverse events (lasting ≥ 7 days); occur at any time while the patient is still receiving study treatment that are either: definitely, probably, or possibly related to either LEE011 or TACE the study will be terminated to enrollment.

Only patients started on the first dose of LEE011 will be included in the evaluation of DLT. If a patient has a DLT that patient will not receive further LEE011. Patients following initial chemoembolization who never receive LEE011 will not be included in the MTD analysis and will be replaced. The patients will be followed for thirty days following the initial chemoembolization for safety assessment. Patients will be enrolled into the next highest drug cohort only after 3 or 6 patients have completed the first cycle of therapy. Once the MTD is determined, patients at the MTD dose will continue with LEE011 and represent the first three patients accrued to the phase II aspect.

Due to observed (TACE related, non DLT) toxicity on cohort 1 specific criteria for cohort 1 has been developed after discussion with the FDA. Cohort 1 has been expanded to 6 patients. Decision for dose escalation will be made using the following criteria:

- No or one DLT: the next three patients will be assigned to next higher dose level (400 mg of LEE011).
- At least two toxicities: the MTD is exceeded and the phase I component of the trial will be stopped with no continuation into the phase II component.

For Cohort 2 and 3 the following traditional 3+3 dose escalation rules will be used:

- If a dose limiting toxicity (DLT) is observed in 1 out of 3 patients at a given dose level, up to 3 additional patients will be enrolled and treated at that dose level.
- If 2 out of 3-6 patients at that dose level have DLTs, the dose will be decreased to the previous dose level, and up to 3 additional patients will be enrolled at that dose level for a total of 6 patients.

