6.12.4 CHEMOEMBOLIZATION PROCEDURAL PREPARATION

- a) The patient is prepped and draped in a sterile fashion.
- b) Carefully evaluate the vascular network associated with the lesion with high resolution imaging prior to beginning the embolization procedure.

- c) DC beads are available in a range of sizes, but only 100 to 500 um particles should be utilized. Care should also be taken to choose the appropriate size of DC bead that bases matches the vascular target or vessel size.
- d) Choose a delivery catheter based on the size of the target vessel. DC bead can tolerate temporary compression of 20% to 30% in order to facilitate passage through the delivery catheter.
- e) Introduce the delivery catheter into the target vessel according to standard techniques. Position the catheter tip as close as possible to the treatment site to avoid inadvertent occlusion of normal vessels.
- f) DC are not radio-opaque. It is recommended to monitor the embolization under fluoroscopic visualization by adding the desired amount of contrast medium to the suspension fluid.
 - a. Take care to ensure proper suspension of the DC bead in the contrast medium to enhance distribution during injection.
 - b. Draw the DC bead into a syringe needle of a size greater than or equal to 19 gauge.
 - c. At a rate no faster than 1ml/minute, slowly inject DC bead into the delivery catheter under fluoroscopic visualization while observing the contrast flow rate. Exercise conservative judgment in determining the embolization endpoint.
- g) Upon completion of the treatment, remove the catheter while maintaining gentle suction so as not to dislodge the DC bead still within the catheter lumen.
- h) Discard any unused DC bead loaded with doxorubicin.

6.12.5 **POST-CHEMOEMBOLIZATION PROCEDURE ORDERS AND CARE**

- a) Admit patients overnight for observation.
- b) Hydration with IV normal saline
- c) Patient controlled analgesia for pain control.

6.12.6 **POST-PROCEDURE CARE**

- a) Post-arteriography bedrest with monitoring of vital signs and pulses.
- b) Patient can be discharged as soon as they demonstrate adequate oral intake or liquids, no longer require parenteral narcotics or antiemetics.
- c) Fevers <103 degrees F are normal during the first week following treatment and do not require cultures.
- d) Following institutional guidelines, patients will be seen in the HCC multidisciplinary clinic 7-10 days following chemoembolization and will have the following evaluations completed:

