7.2.3 Patient Demographics and other Baseline Characteristics

The data that will be collected on patient characteristics at screening includes:

- Demographic (name, date of birth, age), sex, race/ethnicity;
- Diagnosis, RB status, and extent of cancer (staging) – tissue biopsy (required);
- Pertinent Medical History;
- Prior cancer treatment;
- All medications taken within 30 days before first treatment. If there are any changes, medications are to be updated on a continual basis.

Furthermore the following assessments will be performed:

- Vital Signs (BP, HR, T, RR);
- Adverse Events / Conmeds
- Height and Weight;
- Physical Examination (PE);
- ECOG Performance Status (PS);
- Laboratory Evaluations (chemistry, CBC, PT/INR, Lipid Panel, and UA)
- ECG (in Triplicate – baseline only)
- ECHO or MUGA;

- Radiological Assessments (RECIST 1.1) (CT - chest/abdomen/pelvis or MRI – abdomen/pelvis). Chest CT will be performed at baseline only. During the treatment phase, a Chest CT will be performed as clinically indicated;
- Pregnancy Test (Women of Child-bearing Potential Only).

7.2.4 **Pre-Treatment - Biomarker Tissue Biopsy (Required)**

After signing the treatment and biopsy informed consent, the screening biopsy, confirming HCC diagnosis, staging, and (RB+) result, must be complete within 28 days prior to registration unless the patient has archival formalin fixed paraffin embedded tissue to determine RB status. This biopsy is required to confirm patient eligibility. However, initial TACE procedure can be initiated prior to determination of RB status provided informed consent is signed and biopsy tissue is available for analysis.

7.2.5 **Biomarker / DNA Blood Collection (Optional – Phase II only)**

After signing the optional biomarker / DNA consent for future biomarker and DNA blood, samples will be collected at baseline, during treatment, and at the end of treatment or early-term visit. This procedure is for research and will not be used to make medical decisions regarding the patient's treatment.

7.3 **TREATMENT PHASE**

7.3.1 **Study Treatment**

Patients will be treated with chemoembolization once every 4 weeks (or every 28 Days), for a total of up to 4 chemoembolizations within the first 6 months.

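### Phase Ib: section 6.6 sets no minimum exposure beyond the first LEE011 dose, so a DLT-free patient with a shortened first cycle counts as fully evaluable

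*Combined protocol and SAP*

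**What the plan says.** Section 6.6 bases the MTD on DLTs in the first cycle only. Two sentences fix who counts: "Only patients started on the first dose of LEE011 will be included in the evaluation of DLT", and "Patients following initial chemoembolization who never receive LEE011 will not be included in the MTD analysis and will be replaced". The next cohort opens once three or six patients have completed cycle 1, but completion is not defined by doses taken and is not tied to replacement. The recommended phase II dose is the highest level with at most one first-cycle DLT in six patients.

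On timing, section 6.3 states "LEE011 will be given orally once a day on days 1-21 of a 28 day cycle", with days 22 to 28 as rest. Section 6.12.6 says that "patients will be seen in the HCC multidisciplinary clinic 7-10 days following chemoembolization", while the corresponding column of Table 7.1 gives 7 to 14 days. The text on giving LEE011 with chemoembolization, which follows section 6.12.6, says "LEE011 will be initiated at the earliest of 7 days following embolization chemoembolization provided the following criteria are met" and allows up to 28 days to meet those criteria. On repeat procedures, section 6.12.7 says "Repeat Chemoembolization (for either ipsilateral or contralateral disease) if indicated, should be performed at least 4 weeks apart", and section 7.3.1 describes a 28-day interval with up to four procedures in the first six months.

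No section says whether LEE011 is held around a repeat TACE. The nearest statement is a laboratory condition: if liver enzymes are raised after chemoembolization, "decrease to baseline grade is necessary to continue/initiate LEE011". Section 6.9 advises considering an interruption when a caution-list drug is needed briefly. By contrast, footnote 7 of Table 7.1 does order a hold around the optional research biopsy.

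**The concern.** A 3+3 decision assumes that each DLT-free patient was exposed to the dose for long enough to have shown a DLT. Section 6.6 asks only for a first dose. A patient who stops early for a reason unrelated to LEE011 toxicity, with no DLT, enters the count as a full non-event. In a cohort of three that patient is one third of the evidence, and in a cohort of six one sixth. Taken alone, counting such patients makes a dose look safer than the exposure supports.

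Several entries in Table 6.2 sharpen this, because they become DLTs only on recurrence: grade 3 thrombocytopenia without significant bleeding, moderate rises in bilirubin or AST/ALT (which also qualify by slow resolution), and QTcF of 481 ms or more. Lost dosing days leave less opportunity to see a recurrence. The dose chosen in this way is then given to the phase II patients, 40 in all.

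**Working it through.** The plan gives no figure to reproduce; the check is calendar arithmetic.

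**Inputs.** LEE011 on days 1–21 of 28 (6.3). Start no earlier than 7 and no later than 28 days after the first TACE (text after 6.12.6). Clinic visit at days 7–10 (6.12.6) or 7–14 (Table 7.1). Repeat TACE from 28 days (6.12.7, 7.3.1). Missed doses are not made up (6.4). Steady state by about day 8 (1.7.4.1).

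**Assumptions not in the plan.** The repeat is given exactly on day 28. LEE011 is then held for 7 days, borrowing the gap that the plan sets before the initial start. The cycle calendar is not reset by the hold.

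**Formulas.** Let the first TACE be day 0 and C1D1 be day s.

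- Cycle day of the repeat TACE = 28 − s + 1 = 29 − s.
- Doses taken before it = min(21, 28 − s).
- Earliest resumption after a 7-day hold = cycle day (29 − s) + 7 = 36 − s. For s = 8 to 14 this is C1D28 to C1D22, all in the rest week, so no cycle 1 dose is regained.
- Dosing days from C1D8 onward = doses − 7 (a full cycle has 14).

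| LEE011 start (s) | Repeat TACE falls on | Doses with a 7-day hold | Dosing days from C1D8 | Doses with no hold |
|---|---|---|---|---|
| 7 | C1D22 (rest) | 21 (100%) | 14 | 21 |
| 8 | C1D21 | 20 (95%) | 13 | 21 |
| 9 | C1D20 | 19 (90%) | 12 | 21 |
| 10 | C1D19 | 18 (86%) | 11 | 21 |
| 11 | C1D18 | 17 (81%) | 10 | 21 |
| 12 | C1D17 | 16 (76%) | 9 | 21 |
| 13 | C1D16 | 15 (71%) | 8 | 21 |
| 14 | C1D15 | 14 (67%) | 7 | 21 |

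Later starts also overlap: for s = 15 to 28 the repeat falls on C1D14 to C1D1. A single 7-day hold removes at most 7 doses, so 21 − 7 = 14 remains the floor if dosing resumes promptly.

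**How likely is a repeat inside cycle 1?** Cycle 1 ends on day s + 27, which is day 34 to 41 for s = 7 to 14. Section 8.0 schedules the first progression imaging at 8 weeks, day 56. A repeat inside cycle 1 would therefore mostly be one planned in advance, such as treatment of the other lobe. The documents give no frequency.

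**Effect of a minimum share.** 0.70 × 21 = 14.7, so 15 doses; 0.75 × 21 = 15.75, so 16; 0.80 × 21 = 16.8, so 17. In the table above, the 70% rule would replace the day-14 start, 75% days 13–14, and 80% days 12–14. Starts within the 7–10 day clinic window keep 18 to 21 doses and would not be replaced under any of the three.

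**The case against.** The strongest reply is that dose loss through TACE needs three things together, none of them required: a repeat at or near the minimum interval, a LEE011 start after day 7, and a hold of about a week. A repeat is given only if indicated. The 7-day gap governs the initial start, and the wording about continuing LEE011 belongs to a separate enzyme condition. Since the plan writes a hold where it wants one, for the biopsy, it is natural to read that dosing continues through a repeat TACE. Section 6.9 offers only discretionary advice on interruption. Footnote 13 of Table 7.1 also allows a schedule without overlap: a day-7 visit used as C1D1 puts a day-28 repeat on C1D22. All of this stands. A reader might infer that the plan makes a repeat TACE cut cycle 1 short; the documents do not support that.

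A second reply is that the bias need not run one way. That also stands for TACE overlap. Section 9.2 lists events expected after chemoembolization, including raised liver enzymes and infection, and Table 6.2 counts events only possibly related to LEE011. A TACE inside the window can therefore add DLTs.

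A third reply is that cohort opening waits for completed first cycles and that section 16.0 provides real-time escalation review. This stands only in part. Reviewers may notice a short course, but completion is not defined by doses, and section 6.6 allows replacement only of patients who never start.

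The stake is also limited: cohort 1 already has six patients, the recommended dose is defined on six, and the grade 4/5 stopping rule runs beyond cycle 1.

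**Conclusion.** The point holds as a gap in the evaluability rule. Section 6.6 positively includes anyone with a first dose and has no way to replace a DLT-free patient whose cycle 1 was cut short for reasons other than LEE011 toxicity. That is true whatever the cause of the shortfall.

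Repeat TACE is one illustration. At the 28-day minimum with an assumed 7-day hold, starts on days 8–14 leave 20 to 14 of 21 doses, or 20 to 18 for starts on days 8–10. Without a hold the loss is zero. Frequency is unknown, and the effect on escalation cannot be derived from the documents.

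Two stronger conclusions are tempting and not supported. One is that TACE overlap makes a dose look safer. Counting truncated DLT-free courses pushes that way, but added TACE-related events push the other way, and the net direction is unknown. The other is that a repeat TACE must be kept out of the dosing days. That is a clinical trade-off, because phase Ib exists to test the combination. The listing of fentanyl as both TACE sedation (6.12.3) and a prohibited drug (Appendix Table 2) is a separate matter and adds no weight here.

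This is a cheap improvement, not a flaw that undermines the design.

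**What to change.** For phase Ib only, add to section 6.6: *A patient without a DLT who received less than 75% of the 21 cycle 1 doses (fewer than 16) for reasons other than LEE011 toxicity is not DLT-evaluable and is replaced. Any Table 6.2 event at least possibly related to LEE011 still counts.*

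The 75% is an example, not a figure from the documents; 70% (15 doses) or 80% (17 doses) would also serve, provided it is set in advance. Interruptions for LEE011 toxicity remain under Table 6.2, so no real DLT is removed. Phase II is unchanged.

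The cost is an occasional replaced patient. Each replacement takes at least 34 days from that patient's TACE to the end of cycle 1 (7 + 27).

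The investigators may also choose to place a non-urgent cycle 1 repeat TACE in the rest week (C1D22 or later). For starts on days 7–14 a C1D22 repeat is s − 7 = 0 to 7 days later than the minimum, but it reduces concurrent exposure to LEE011 and TACE. That is an option, not a required correction.
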